- The quantitative amount of oxygenated/deoxygenated hemoglobin in the intestinal wall determined by MSOT differs between fasting persons and persons after ingestion food.
- The quantitative amount of oxygenated/deoxygenated hemoglobin in the intestinal wall determined by MSOT changes after the ingestion of food.
- The postprandial changes in the quantitative amount of oxygenated/deoxygenated hemoglobin in the intestinal wall determined by MSOT occur successively in subsequent sections of the gastrointestinal tract, from oral to aboral.
- A relationship exists between postprandial changes in the quantitative amount of oxygenated/deoxygenated hemoglobin in the wall of the gastrointestinal tract determined by MSOT and postprandial changes in Doppler sonographic signals in the major splanchnic arteries (truncus coeliacus, superior mesenteric artery, inferior mesenteric artery).
- The postprandial changes in the quantitative amount of oxygenated/deoxygenated hemoglobin in the intestinal wall determined by MSOT are associated with the presence of chyme in the lumen of the gastrointestinal tract.
- Measurement of ICG signals within the lumen of the gastrointestinal tract using MSOT after ingestion of ICG-containing food indicates the presence of chyme within the lumen of the gastrointestinal tract.
- A relationship exists between postprandial changes in the quantitative amount of oxygenated/deoxygenated hemoglobin in the wall of the gastrointestinal tract determined by MSOT and postprandial changes in the ICG signal determined by MSOT within the lumen of the gastrointestinal tract after ingestion of ICG-containing food.

Primary objectives:

- Comparison of oxygenated/deoxygenated hemoglobin signal in the wall of the gastrointestinal tract measured by MSOT between fasting subjects and subjects after ingestion of food.

Secondary objectives:

- Measurement of the postprandial change in the oxygenated/deoxygenated hemoglobin signal in the wall of the gastrointestinal tract measured by MSOT over time and over the different sections of the gastrointestinal tract.
- Comparison of the Doppler sonographic signal in the large arteries of the splanchnic area between fasting subjects and subjects after ingestion of food.
- Measurement of the postprandial change in the Doppler sonographic signal in the large splanchnic arteries over time and over the different splanchnic arteries.

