- Correlation between postprandial changes in the oxygenated/deoxygenated hemoglobin signal in the wall of the gastrointestinal tract measured by MSOT and postprandial changes in Doppler sonographic signals in the large arteries of the splanchnic artery.
- Comparison of the ICG signal in the lumen of the gastrointestinal tract measured by MSOT between fasting subjects, subjects after ingestion of food and subjects after ingestion of food containing ICG.
- Measurement of the postprandial change in the ICG signal in the lumen of the gastrointestinal tract measured by MSOT over time and over the different sections of the gastrointestinal tract in subjects after ingestion of food containing ICG.
- Correlation between postprandial changes in the oxygenated/deoxygenated hemoglobin signal in the wall of the gastrointestinal tract measured by MSOT and postprandial changes in the ICG signal in the lumen of the gastrointestinal tract measured by MSOT in subjects after ingestion ICG-containing food.

Study type

Since no data exist to support the hypothesis of this study to date, it is an exploratory study.

6. Target parameters

Study related measures and target
All MSOT measurements are taken over the gastric antrum, terminal ileum, transverse colon, and sigmoid colon.
Primary targets (obligatory):
Quantitative de-/oxygenated hemoglobin signal (in arbitrary units)
These target values are collected non-invasively using MSOT.
Secondary targets:
Qualitative and quantitative ICG signal (in arbitrary units)
Quantitative single wavelengths signal (in arbitrary units)
Optoacoustic spectrum (in arbitrary units, normalized)
These target values are collected non-invasively using MSOT.
Secondary targets (optional):
Doppler sonographic signals of the coeliac trunk, superior mesenteric artery, inferior mesenteric artery:

• Doppler sonographic spectrum• Doppler sonographic curve• Velocity profile• Flow profile• Flow volume• Resistance index• Pulsatility index
These target values are collected non-invasively using sonography.

7. Study design

Monocentric / multicentric

It is a monocentric diagnostic study with prospective data collection (Investigator Initiated Trial, IIT).

Study arms:

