A comparison is made between 3 study arms: A: Fasting, B: Standardised breakfast, C: Standardised breakfast with added ICG (250mg in 50ml aqua). As part of the crossover design, each subject will pass through all three study arms on three different days. There is a period of at least 48 hours between two consecutive study days for each subject.

Randomisation

Randomisation is not planned. As part of the crossover design, each subject passes through all three study arms. The order of the study arms is identical for each subject:

1. Study arm A: Fasting
2. Study arm B: Standardised breakfast
3. Study arm C: Standardised breakfast with added ICG

Blinding

No blinding is planned.

8. Study population

Inclusion and exclusion criteria

Inclusion criteria:

- Age over 18 years
- Written declaration of consent

Exclusion criteria

Generally valid:

- Pregnancy
- Nursing mothers
- Tattoo in the field of investigation
- Subcutaneous fat tissue over 3 cm
- Chronic or acute diseases of the gastrointestinal tract or symptoms suggestive of such a disease
- Diseases requiring acute treatment
- Lack of written consent

ICG related:

- Known hypersensitivity to ICG, sodium iodide or iodine
- Hyperthyroidism, focal or diffuse thyroid autonomy
- Treatment with radioactive iodine for the diagnostic examination of thyroid function within two weeks before or after the study
- Restricted renal function
- Intake of the following drugs: Beta-blockers, anticonvulsants, cyclopropane, bisulphite compounds, haloperidol, heroin, meperidine, metamizole, methadone, morphine, nitrofurantoin, opium alkaloids, phenobarbital, phenylbutazone, probenecid, rifamycin, any injection containing sodium bisulphite.

Subject number

As this is a pilot study, it is not possible to calculate the exact number of cases. It is planned to examine a total of 10 study subjects.

Recruitment measures

Volunteers will be informed by means of a public notice and via the homepage of the University Hospital Erlangen. If volunteers are willing to participate, they will be fully informed about the aims and methods (especially about the scientific/explorative nature of the study), the benefits and risks and the revocability of participation in the study. Each participant receives an expense allowance of 150€.

9. Study course

Procedure for informing about and obtaining consent

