The study starts for the participants at 10 pm on the day before the first examination day with adherence to the fasting period. On the first examination day, the preprandial measurement is performed at 8 am after 10 hours of fasting in all study arms. The preprandial measurement starts with the sonographic localisation of the sections of the gastrointestinal tract that will be examined in the following measurements with MSOT and Doppler sonography. Skin markings are made with a skin-compatible marker pen for better reproducibility of the following measurements. The further procedure of the preprandial measurement and each of the following postprandial measurements will follow an identical measurement protocol. A period of 20 minutes is planned for each measurement protocol. Depending on the study arm, the subjects remain fasting throughout all the measurements of the day (study arm A) or receive a standardised breakfast with or without ICG supplement (study arm B/C) 30 minutes after the start of the preprandial measurement. After the subjects have eaten the breakfast within 15 minutes, the first postprandial measurement takes place exactly 60 minutes after the preprandial measurement in all study arms. In the following 6 hours, further postprandial measurements are taken at 60-minute intervals, so that the last measurement takes place exactly 7 hours after the start of the preprandial measurement. 4 hours after breakfast, the subjects from study arms B and C receive another standardised meal to simulate regular food intake. This meal does not contain ICG. The subjects in study arm A remain fasting throughout all the measurements of the day.

On each measurement day two subjects are examined in parallel with a time offset of 30 minutes. This means that the entire examination for the second participant begins at 8:30 am.

[figure not shown]

Figure 1: Course of one examination day for one participant. X-axis is time in minutes with 0 being the beginning of the preprandial measurement at 8:00 or 8:30 am..

In a crossover design, each participant is examined on three measurement days according to the three study arms. There must be a minimum time interval of 48 hours between each examination day for the participant. The order of the examination days is predetermined:

1st examination day (study arm A): Fasting

2nd examination day (study arm B): Standardised breakfast

3rd examination day (study arm C): Standardised breakfast with ICG

[figure not shown]

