In addition, the study will be terminated for the individual participant if, as a result of adherence to the fasting period before the measurements and during the measurements in study arm A, complaints such as malaise, weakness, a strong feeling of hunger, stomach complaints, abdominal cramps or similar occur.

Termination criteria for the whole study:

A termination of the entire study is not planned

Statement on medical justifiability

Based on previous experience, the risk of undesired events associated with is considered extremely low.

No serious event has been reported so far, neither at our own site nor in literature. The majority of the reported (foreseeable) problems related either to the use of ultrasound gel for examination or the need to wear eye protection. The use of filter glass also explains the reported red-sightedness. This phenomenon was reversible within seconds. Table 1 shows the reported events from our study (MSOT_DMD, 67_18 B, Clinicaltrials.gov Identifier: NCT03490214).

	Muscular dystrophy Duchenne N=10	Healthy volunteer N=10
Reversible adverse events- no.		
Pressure of safety goggles	2 (20%)	
Coolness of Ultrasound-gel		4 (40%)
Red cast view		1 (10%)
Serious adverse events- no.	0 (0%)	0 (0%)

Table 1 – Reported events MSOT_DMD, 67_18 B

The occurrence of adverse side effects from the systemic use of ICG (Verdye, Diagnostic Green 5mg/ml) is very rare (<1 in 10 000). According to the manufacturer, the dye is not absorbed after oral application of ICG and is not subject to enterohepatic circulation. Therefore, the occurrence of systemic side effects from oral intake of ICG is very unlikely.

10. Biometrics

Explorative study: explanation of the statistical methodology, justification of the selected number of cases

Case number calculation:

As this is a pilot study and no information on the expected differences between the different groups is available yet, no case number calculation was performed. The number of cases given represents an estimate or is within the appropriate range for a pilot study.

Statistical methods:

The data is given as mean value with standard deviation. Correlations are given with the non-parametric Spearman correlation coefficient (R_s). According to the distribution on groups the differences of the mean values are examined statically with a nonparametric T-test (Mann-Whitney test) or ANOV. In all analyses an error level of <0.05 is considered statistically significant.

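### The same 10 subjects are measured fasting and fed, but the plan names an independent-groups test or an unspecified ANOV and no paired method

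*Combined protocol and SAP*

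**What the plan says.** Section 7 (Study arms) sets up a crossover of three conditions, fasting (A), standardised breakfast (B) and breakfast with ICG (C), in which "each subject will pass through all three study arms on three different days". Section 9 (Time schedule) repeats this: "In a crossover design, each participant is examined on three measurement days according to the three study arms". Section 8 plans 10 subjects. Under Randomisation, Section 7 adds: "The order of the study arms is identical for each subject".

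The primary objective in Section 5 is: "Comparison of oxygenated/deoxygenated hemoglobin signal in the wall of the gastrointestinal tract measured by MSOT between fasting subjects and subjects after ingestion of food".

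On each day "the preprandial measurement is performed at 8 am after 10 hours of fasting in all study arms". The first postprandial reading follows 60 minutes later, and over the next six hours "further postprandial measurements are taken at 60-minute intervals". That makes one preprandial and seven postprandial readings per subject-day, at four bowel sections.

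Section 10 gives one sentence on testing differences: "the differences of the mean values are examined statically with a nonparametric T-test (Mann-Whitney test) or ANOV". It applies a 0.05 significance level to all analyses. The supplied text mentions no signed-rank test, paired t-test, Friedman test, repeated-measures ANOVA, mixed model or subject factor. It does not say how the eight readings of a day are reduced for the test.

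**The concern.** The fasting and fed values come from the same people, so they are paired. Mann-Whitney takes its reference distribution from two independent samples, and its p-value therefore ignores the pairing. An ANOVA with a subject factor would respect the design and a one-way ANOVA would not. The text does not say which is meant.

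This is the primary comparison, and there are only 10 subjects. The main statistical benefit of measuring each person three times is that stable differences between people drop out of the contrast. An analysis that ignores the pairing can give that benefit away. If repeated readings are also treated as separate observations, it can go wrong in the other direction and declare differences too often.

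**Working it through.** The plan has no figure to reproduce: Section 10 states that no case number calculation was done, and no effect, SD or correlation is given.

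**Inputs.** From the documents: n = 10, the same subjects in each arm, significance level 0.05, one preprandial and seven postprandial readings per day. Assumed: two-sided testing, normal data, total SD 1, the correlation ρ between days, the shift, and the variance shares in case 3.

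**1. One value per subject and arm.** The true variance of the mean difference is 2(1 − ρ)/n. An unpaired test works as if it were 2/n. The ratio is 1 − ρ, so at ρ = 0.5 the true variance is 0.10 and the assumed one is 0.20. For ρ > 0 the unpaired test is therefore too cautious.

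Simulation used value = subject effect (variance ρ) + residual (variance 1 − ρ). The exact Mann-Whitney test rejects at U ≤ 23 (size 4.33% for independent groups) and the exact signed-rank test at W ≤ 8 (size 4.88%). Power is for a shift of 0.8 SD:

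| ρ | Mann-Whitney actual type I error | Mann-Whitney power | Signed-rank power | Gap (points) |
|---|---|---|---|---|
| 0 | 4.3% | 35% | 34% | −1 |
| 0.3 | 2.0% | 33% | 46% | 13 |
| 0.5 | 0.9% | 32% | 60% | 28 |
| 0.7 | 0.2% | 31% | 81% | 50 |
| 0.8 | below 0.1% | 31% | 93% | 62 |
| 0.9 | about 0 | 31% | 99.8% | 69 |

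The signed-rank test keeps its type I error near 5% throughout. In terms of detectable difference at 80% power, an independent-groups t-test needs 1.32 SD. A paired t-test needs 0.996 × √(2(1 − ρ)), which is 1.18, 1.00 and 0.77 SD at ρ = 0.3, 0.5 and 0.7.

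**2. Change score: mean of the seven postprandial readings minus the same-day preprandial reading.** If subjects differ only by a constant level, that level cancels. The change scores are then uncorrelated between days, with variance (1 − ρ)(1 + 1/7). At ρ = 0.5 this is 0.571, SD 0.756, so a shift of 0.8 becomes 0.8/0.756 = 1.06 SD of the change score. Power is 56% (Mann-Whitney) against 54% (signed-rank). At ρ = 0.8 it is 92% against 90%. Mann-Whitney type I error is 4.1% to 4.5%. Pairing gains nothing here.

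These powers assume that the shift is present in all seven readings. Section 4 expects the ileum to respond after 120 minutes at the earliest and the colon after about 240 to 300 minutes. With the shift only in the last three readings, power at ρ = 0.5 is 14% against 15%. The absolute values change; the lack of gain from pairing does not.

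**3. Seven hourly values pooled as 70 against 70 independent observations.** With variance shares s (subject), d (day) and e = 1 − s − d, the true variance of the difference of arm means is 2(d + e/7)/10. Treating the readings as independent gives about 2/70 = 0.0286.

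| s / d | True variance | Ratio to 0.0286 | Simulated type I error |
|---|---|---|---|
| 0.5 / 0.2 | 2(0.2 + 0.3/7)/10 = 0.0486 | 1.7 | about 16% |
| 0.3 / 0.3 | 2(0.3 + 0.4/7)/10 = 0.0714 | 2.5 | about 21% |
| 0.5 / 0 | 2(0 + 0.5/7)/10 = 0.0143 | 0.5 | about 1% |

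Repeat runs of the pooled case differed by one or two percentage points.

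**The case against.** Three arguments can be made for the plan.

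First, ANOV may be shorthand for a repeated-measures ANOVA. That is possible, and the documents do not support the inference that an independent-groups ANOVA was intended. But the only fully named test is the unpaired one, and the stated basis for choosing between the two is the distribution, not the pairing. On the kindest reading, one of the two permitted routes still ignores the design.

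Second, the study is a pilot. Section 5 says: "Since no data exist to support the hypothesis of this study to date, it is an exploratory study". No decision rule hangs on the p-value. This limits the consequences and explains the absence of a sample size calculation. It does not make paired values independent, and the plan still declares significance at 0.05 in every analysis.

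Third, the loss may be nil. That stands: at zero correlation between days, or with a change score that cancels a constant subject level, the unpaired test loses nothing. The documents do not say whether either situation applies.

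Two stronger readings are tempting. A reader might infer that the harm is confined to lost sensitivity. That holds for one value per subject and arm, and the plan does not commit to that. A reader might equally infer that false positives are to be expected. Nothing in the plan says that the hourly values will be pooled; it only fails to exclude it.

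**Conclusion.** The point holds. The named rank test does not fit the within-subject design, and no paired alternative is given in the supplied text. The direction and size of the error cannot be settled from the documents, because the value entering the test is not stated.

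The illustrations run from no loss, through 28 points of power at ρ = 0.5, to type I error of about 16% to 21% under pooling with a day effect. All rest on assumed correlations, shifts and variance shares. The largest gap in the table should not be read as a limit for this trial: it is 62 points if the grid stops at ρ = 0.8 and 69 points at 0.9. The mismatch between design and test does not depend on any of these assumptions.

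This should be fixed before analysis. In an exploratory pilot without a decision rule it is not more serious than that.

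**What to change.** Replace the testing sentence in Section 10 with wording such as:

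> Fed versus fasting is compared within subject, on one pre-specified summary per subject-day, bowel section and haemoglobin signal, with the paired t-test (mean paired difference with 95% CI) or the Wilcoxon signed-rank test (Hodges-Lehmann estimate with 95% CI), one to be named in advance. Three-arm and time-course comparisons use a repeated-measures method (a mixed model with subject and subject-by-day random effects; Friedman only for three arms on one summary value). Hourly values are not pooled as independent observations.

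The sponsor has to fill in the summary, for example the raw postprandial value or the change from the same-day preprandial value. Each test should keep its own estimate: a mean difference belongs with the t-test and a Hodges-Lehmann estimate with the signed-rank test.

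The cost is wording only, with no added subjects, visits or measurements. If the between-day correlation of the summary is zero, the signed-rank test gives up about 2 to 3 percentage points of power at most against Mann-Whitney (for example 73% to 74% against 76% at a shift of 1.33 SD).

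Pairing does not remove the confounding of arm with study day that comes from the fixed A-B-C order. That is a separate limitation and should be stated as one.
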